### 3.3 ANALYSES FOR SECONDARY ENDPOINTS

#### Phosphorylated HSP27 (PD endpoint)

Phosphorylated HSP27 (pHSP27) and total HSP27 (tHSP27) in peripheral whole blood with ex-vivo sorbitol stimulation and in skeletal muscle (without sorbitol stimulation) will be measured at the time points specified in the schedule of assessments (Tables 2 and 3 of the protocol).

The Visit 4 (pre-treatment) value will be defined as the baseline value for change from baseline calculations.

All pHSP27 and tHSP27 values will be transformed using the natural logarithm function and will be summarized at each visit. If there is any value reported as zero (0) in either of the two parameters, a factor of 0.01 will be added to all observations prior to the log transformation.

The change from baseline in pHSP27, tHSP27 and pHSP27/tHSP27 - in sorbitol stimulated whole blood and in muscle - will be summarized at each post-treatment timepoint. The geometric mean for fold change from baseline and percent change from baseline (and 95% confidence interval) in pHSP27/total HSP27 will be calculated for each post-treatment timepoint. The percent change from baseline will be calculated as:

Percent change from baseline =  $100 * (\exp(\text{mean of change from baseline on the log-transformed scale}) - 1)$ .

Post-treatment will be also obtained at the estimated  $C_{\max}$  time (e.g. 4h+-1h).

Summaries presented for subjects with second muscle biopsy at 4 weeks post-treatment (Biopsy Cohort Week 4), 8 weeks post-treatment (Biopsy Cohort Week 8), and for all subjects combined.

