### **10.3 Secondary Study Parameter(s)**

#### **10.3.1 PD Endpoints**

PD parameters include target engagement in pHSP27 as measured in peripheral whole blood after sorbitol stimulation ex vivo and in skeletal muscle needle biopsies without ex vivo stimulation.

PD endpoints will be summarised by timepoint. Natural log (ln) transformed values of pHSP27 will be analysed using paired t-test or similar methods. The difference between the post dose log transformed pHSP27 value and the baseline log transformed value will be tested versus zero.

Point estimates for the difference will be presented along with 95% CIs. Estimates will be back transformed using the exponential function to estimate the ratio of post dose pHSP27 value to baseline value. Further details of the PK/PD analysis of pHSP27 will be specified in the SAP.

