## 2 STATISTICAL CONSIDERATIONS

### 2.1 GENERAL CONSIDERATIONS

All descriptive statistics for continuous variables will be reported using mean, standard deviation (SD), median, minimum, and maximum. Standard error (SE) will be reported for all change from baseline tables. Categorical variables will be summarized as number of subjects and their percentages.

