### 3.2.3 Clinical Laboratory Parameters

Laboratory values that are non-missing and reported as 'below the detectable limit' of an assay will be replaced by  $\frac{1}{2}^*\text{LLOQ}$ . Values that are reported as 'above the detectable limit' will be replaced by  $1.5^*\text{ULOQ}$ , to allow for summary tables to be generated. Laboratory results will be summarized using International System of Units (SI).

For all quantitative parameters listed in Section 8.1.1 of the protocol, the actual value and the change from baseline to each post-baseline visit and to the end of treatment will be summarized by visit, using descriptive summary statistics. Qualitative parameters will be summarized using frequencies (number and percent of subjects), and changes from baseline to each post-baseline visit and to end of treatment will be reported using shift tables. Percentages will be based on the number of subjects with both non-missing baseline and relevant post-baseline results.

Laboratory test results will be assigned an LNH classification according to whether the value is below (L), within (N), or above (H) the laboratory parameter's reference range. Within-treatment comparisons for each laboratory parameter will be based on 3-by-3 tables (shift tables) that compare the baseline LNH classification to the LNH classification at each post-baseline visit and at the end of treatment. Similar shift tables will also compare the baseline LNH classification to the LNH classification for the highest and lowest value during the treatment period.

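### If any HSP27 value is zero, the SAP adds a fixed 0.01 to every observation before taking logs, so the geometric-mean change and its CI depend on the assay's reporting unit

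*SAP*

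**What the plan says.** SAP 3.3, under phosphorylated HSP27, log-transforms the raw assay values: "All pHSP27 and tHSP27 values will be transformed using the natural logarithm function and will be summarized at each visit". The rule for zeros has a trigger, "If there is any value reported as zero (0) in either of the two parameters", and an action, "a factor of 0.01 will be added to all observations prior to the log transformation". The two parameters are pHSP27 and total HSP27, in stimulated whole blood and in unstimulated muscle.

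The reported quantities are the geometric-mean fold change and the "percent change from baseline (and 95% confidence interval) in pHSP27/total HSP27 will be calculated for each post-treatment timepoint". The percent change is 100 × (exp(mean log change) − 1). Summaries are given for each biopsy cohort and for all subjects combined.

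Protocol 10.3.1 uses the same log scale and back-transformation, has no offset, and adds a test: "The difference between the post dose log transformed pHSP27 value and the baseline log transformed value will be tested versus zero".

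Two other SAP rules bear on this. In SAP 3.2.3, clinical laboratory values "reported as 'below the detectable limit' of an assay will be replaced by" half the LLOQ; that rule is not extended to HSP27. SAP 2.1 requires the median, minimum and maximum alongside the mean for continuous variables.

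**The concern.** Fold change is used because the unit cancels. A constant added to numerator and denominator stops it cancelling. A zero is placed at ln(0.01), and its distance from that subject's other value depends on the unit chosen by the laboratory and on the subject's level. The documents give no HSP27 unit, no LLOQ and no reason for 0.01.

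The error has no fixed direction:

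- A post-dose pHSP27 zero exaggerates the reduction and widens the CI.
- A baseline pHSP27 zero, or a post-dose total HSP27 zero in the ratio, masks or reverses a reduction.
- Because every observation is shifted, true changes in non-zero values shrink when levels are near 0.01.

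The scope is also unclear. The text does not say whether a zero in muscle triggers the offset in blood, or whether a total HSP27 zero triggers it for pHSP27.

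At stake is the estimate of target engagement in blood and muscle, a secondary objective. The protocol expects a 40 to 70% pHSP27 reduction at this dose (Protocol 6.5), and the distortions shown below are large relative to that range.

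**Working it through.** The documents give no numerical result for this endpoint, so there is no figure to reproduce. The check is algebra followed by constructed cases.

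**Algebra.** Multiply the unit by k. The log change becomes ln[(k·post + 0.01)/(k·base + 0.01)]. Without the offset k cancels; with it, k does not. With one post-dose zero among n subjects and all other values well above 0.01, a k-fold unit change multiplies the geometric-mean fold change by about k^(−1/n). For k = 1000 that is 0.61 at n = 14 and 0.37 at n = 7.

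**Inputs.** From the documents: n = 14 enrolled (Protocol 4.4), and up to 8 per biopsy cohort (SAP 3.4.1), so 7 if the 14 split evenly. Assumed: one zero, baseline level S in reporting units, and no other between-subject variation.

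**Formulas.** d = ln[(post + 0.01)/(base + 0.01)]; reported change = 100 × (exp(mean d) − 1); CI limits = exp(mean d ± t(0.975, n−1) × SD/√n) − 1. For n = 14, t = 2.160.

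**One case in full** (post-dose zero, true −50% in the other 13):

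- S = 1: thirteen values of ln(0.51/1.01) = −0.683 and one of ln(0.01/1.01) = −4.615. Mean −0.964, SD 1.051, half-width 2.160 × 1.051/√14 = 0.607. Result −61.9% (−79.2 to −30.1).
- S = 1000: thirteen values of −0.693 and one of ln(0.01/1000.01) = −11.513. Mean −1.466, SD 2.892, half-width 1.670. Result −76.9% (−95.7 to +22.6).

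**All n = 14 cases, % change (95% CI):**

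| S | Post-dose zero, true 0% | Post-dose zero, true −50% (paired t p) | Baseline zero, true −50% |
|---|---|---|---|
| 1 | −28.1 (−64.7, +46.6) | −61.9 (−79.2, −30.1), p = 0.0045 | −29.8 (−65.6, +43.1) |
| 100 | −48.2 (−87.5, +114.6) | −72.8 (−92.7, +1.3), p = 0.052 | −3.5 (−76.7, +299.9) |
| 1000 | −56.1 (−92.6, +159.7) | −76.9 (−95.7, +22.6), p = 0.080 | +13.8 (−80.7, +572.5) |

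The back-transformed median in the −50% cases stays between −49.5% and −50.0%. If total HSP27 is unchanged within subject, the pHSP27-zero figures apply to the ratio as well. A post-dose total HSP27 zero gives the baseline-zero column for the ratio if total HSP27 is also at level S.

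**Biopsy cohorts, n = 7, true −50%.** Post-dose zero: −71.2% at S = 1 and −89.3% at S = 1000. Baseline zero: −2.4% and +159.0%.

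**Low levels.** A fall from 0.05 to 0.02 is truly −60%. With the offset it becomes ln(0.03/0.06), or −50.0%, at a visit without the zero. At the visit with the zero, the mean of thirteen ln(0.03/0.06) and one ln(0.01/0.06) gives −53.8%.

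**With between-subject variation.** A second illustration assumed a true fold change of 0.45, baseline pHSP27 about 1 unit, total HSP27 about 4 units, log-SD 0.2 to 0.3 and n = 14. With no zero and no offset the ratio change is −55.0% (−60.4 to −48.8) in every unit. With one post-dose zero it is −66.0% (−81.3 to −38.1) in the base unit, −79.5% (−96.1 to +7.3) with values multiplied by 1000, and −5.4% (−6.8 to −4.0) with values multiplied by 0.001.

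**The case against.** The strongest reply is that the rule may never be used. Blood is stimulated before assay, the expected reduction leaves 30 to 60% of the signal, and a zero outside a given comparison hardly matters: the true −50% then reads −49.5% at S = 1 and −50.0% at S = 100. That limit is real, but a pre-specified rule has to work when it is triggered, and the SAP foresaw zeros.

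The assay reports in one unit, and the details may sit in the study reference manual, so 0.01 could be suitable. If it happened to equal half the LLOQ, the zero would be placed much as LLOQ/2 places it: at S = 1 the SAP rule is nearly the same as LLOQ/2 with the LLOQ at 2% of baseline (−62.2%, −79.3 to −30.9). Nothing in the two documents shows this, and the shift to non-zero values would remain.

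The change from a CI that excludes no effect to one that includes it depends on the assumed effect. At n = 14 and S = 1000 it does not occur for a true −60% (−96.3 to −3.7) or −70% (−97.1 to −29.5). At n = 7 it does: for −60% the CI goes from (−93.5, −12.5) at S = 1 to (−99.8, +257.5) at S = 1000, and for −70% from (−94.3, −37.6) to (−99.8, +152.7).

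The study is descriptive. Protocol 2.3 and SAP 2.4 exclude formal testing, and SAP 3.3 does not carry over the test in Protocol 10.3.1. So the p-values carry little weight, but the point estimate and CI are the reported result. The median, minimum and maximum would expose a zero without correcting either.

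Adding 0.01 to the dimensionless ratio would remove the unit dependence (−60.4% in every unit in the second illustration), but the text applies the offset to the two raw parameters.

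**Conclusion.** The concern holds. Whenever a zero is present, the geometric-mean change and CI for pHSP27 and for pHSP27/total HSP27 depend on the reporting unit. With n = 14 and one post-dose zero, a true −50% is reported as anything from −61.9% to −76.9% for S between 1 and 1000, and the CI excludes no change at one end and includes it at the other. With a baseline zero, the range is −29.8% to +13.8%. The distortion is larger in the biopsy cohorts.

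One post-dose zero cannot by itself create a conclusive false effect: with no other change or variation, the paired t statistic is 1 in size whatever the unit, and the CI always includes no change. The main harm is a distorted estimate and a CI wide enough to hide a real effect.

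The sizes rest on assumed levels, one zero, and little or no between-subject variation; the unit dependence itself does not. Because it is conditional and concerns a secondary descriptive endpoint, it should be corrected but does not threaten the primary safety objective.

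**What to change.** Replace the offset sentence in SAP 3.3 with a rule of this kind: non-zero pHSP27 and total HSP27 values are analysed as reported; a zero is replaced, before the log transformation, by LLOQ/2 for that assay and matrix, or by half the smallest positive value for that assay and matrix if no LLOQ exists. This follows the approach of SAP 3.2.3 and settles the scope. Report the number of replaced values by parameter, matrix and visit, and show the back-transformed median fold change beside the geometric mean.

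The result is then the same in every unit. For n = 14, true −50%, with the LLOQ expressed as an assumed share of the baseline level:

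| LLOQ | One post-dose zero | One baseline zero |
|---|---|---|
| 5% | −59.6 (−74.6, −35.9) | −34.9 (−63.2, +15.0) |
| 20% | −55.4 (−65.2, −42.9) | −41.1 (−58.7, −15.9) |

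At an LLOQ of 1% of baseline, the post-dose case is −64.0 (−82.3, −26.8). So the substituted value keeps some influence, more so for a low LLOQ, and the fallback depends on the data. The count and the median make that visible.

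The cost is one or two sentences in the SAP and one count row in the PD tables. No new data are needed.

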#### Plasma and muscle PK parameters of losmapimod (PK endpoint)

There will be no PK parameters calculated. Plasma and muscle concentrations of losmapimod will be summarized by time point. Individual concentrations will be plotted versus time using both linear and log scales for the y-axis. Additionally, concentration versus time curves will be plotted as a spaghetti plot. Individual subject listings will also be provided.

Summaries presented for subjects with second muscle biopsy at 4 weeks post-treatment (Biopsy Cohort Week 4), 8 weeks post-treatment (Biopsy Cohort Week 8), and for all subjects combined.

### 3.4 ANALYSES FOR EXPLORATORY ENDPOINTS

For all exploratory endpoints, in addition to descriptive statistics, graphical approaches - such as box plots, forest plots, scatter plots and spaghetti plots - may be used to describe the data.

#### 3.4.1 Assessment of DUX4 Activity

A subset of DUX4-gene transcripts will be measured in skeletal muscle biopsies, using validated QRT-PCR assays, to measure the treatment effect of losmapimod on aberrant DUX4 activity. A composite DUX4 score will be derived for each patient, at each time point based on normalized gene expression values for the panel of pre-selected genes.

The quantification of gene expression using qPCR, normalization of qPCR and derivation of the composite DUX4 score are conducted at a central laboratory (Q2 Lab Solutions). For details on assay validation, gene subset selection criteria/process, and derivation of the composite DUX4 Score, see Appendices 1 – 5.

All subjects will undergo up to two muscle biopsies; one at baseline, pre-treatment (Visit 4, Week 8 ± 1 week), the second on-treatment muscle biopsy approximately 4 or 8 weeks later (Visit 5, Week 14 ± 2 weeks). Up to 8 subjects will have the second on-treatment biopsy at 4 weeks (Biopsy Cohort Week 4) and up to 8 subjects will have the second on-treatment biopsy at 8 weeks (Biopsy Cohort Week 8).

The DUX4 composite score will be summarized as change from pre-treatment (Week 8 biopsy) to on treatment (Week 14 ± 2 weeks). If the pre-treatment or on-treatment DUX-4 results are unavailable, then the assessment is considered missing. Missing results will be imputed by mean, worst case, and median methods ([Section 2.3.6](#)).

The individual components of the composite DUX4 score will also be summarized at each timepoint, along with change from baseline for post-treatment visits.

An additional DUX4 composite score based on a simple average, across all 6 genes, per subject, per timepoint, will be summarized as change from pre-treatment (Week 8 biopsy) to on treatment (Week 14 ± 2 weeks), to assess if a simpler approach to creating a composite score leads to equivalent interpretations of study results.

Similarly, another additional DUX4 composite score based on a simple average, across the top 2 genes, per subject, per timepoint, will be summarized as change from pre-treatment (Week 8 biopsy) to on treatment (Week 14 ± 2 weeks).

Composite scores based on simple averages will not be imputed. Summaries presented for Biopsy Cohort Week 4, Biopsy Cohort Week 8, and overall.

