#### **10.1.1 Analysis Methods**

In general, all study endpoints will be summarised using descriptive statistics. Descriptive statistics for continuous data will include number of subjects (n), mean, standard deviation, median, minimum, and maximum. Plasma concentrations of losmapimod will be summarised by timepoint. Summaries of change from baseline variables will include only subjects who have both a baseline value and corresponding value at the timepoint of interest. Baseline is defined as the pre-treatment period and all values prior to losmapimod treatment. Descriptive statistics for categorical data will include frequency and percentage. Where appropriate, descriptive statistics may be presented with 95% CIs.

Listings will be provided for all collected study data.

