## DOCUMENT REVISION HISTORY

VERSION	DATE	AUTHOR/ UPDATED BY	COMMENTS
V1.0	11-MAR-2020	NA	NA
V1.1	20-JUL-2020	[REDACTED]	
1. Added three exploratory endpoints in section 1.2.3:
 

3. Skeletal muscle tissue replacement by fat using whole-body MRI

• Lean Muscle Volume (LMV)

• Muscle Fat Fraction (MFF)

• Muscle Fat Infiltration (MFI)

 
2. Added some endpoints in section 4.1 IA#2 analysis, see below:
 

• Summary tables of classic TUG and FSHD-optimized TUG.

• PK Summaries

• Summary table of muscle strength by quantitative dynamometry

• Summary table of distance of walking measured by 6-MWT

• Summary table of reachable work space (RWS)

• Summary table lung ventilator function as measured by Spirometry

• Summary table of physical function by MFM

• Summary table of FSHD-HI total score

• Summary table patient global impression of change

• Summary table of FSHD-RODS total score

 
Updated “Lean Muscle Mass” to “Lean Muscle Volume” in section 4.1 IA#2 analysis
 
3. Added more details for derivation of composite MRI endpoints in Appendix 6

			
4. Added muscle PK parameters of losmapimod in section 1.2.2 and section 3.3
 
5. <del>Added “ratio to baseline” analysis for pHSP27/total HSP27</del>
 
6. Added missing data handling rule for missing DUX4 composite score in section 2.3.5
 
7. Deleted the summary of “the reasons for screen failure” in section 3.1.1
 
8. Deleted “number of years the subject had the disease” and “duration of time from diagnosis to the start of losmapimod” and updated “number of D4Z4 repeats” to “number of FSHD repeats” in section 3.1.3

V1.2	13-AUG-2020	[REDACTED]	
1. Added “median imputation” in section 2.3.5 for “DUX4 COMPOSITE SCORE”

V2.0	25-SEP-2020	[REDACTED]	
1. Removed muscle PK parameters of losmapimod in section 1.2.2 and section 3.3 in order to align with protocol version 3.
 
2. Removed muscle fat fraction (MFF) and muscle fat infiltration (MFI) parameters in section 1.2.3 in order to align with protocol version 3.
 
3. Updated appendix 4 to add 6th gene for the subset and steps for determining the top 2 transcripts.

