#### DUX4 COMPOSITE SCORE

Missing composite score will be imputed by three methods as follows

1. Mean Imputation: For subjects missing “pre”, impute using the MEAN(pre) of non-missing subjects. For subjects missing “post”, impute using MEAN(post) from non-missing subjects.
2. Worst case imputation: For subjects missing “pre”, impute using MIN(pre) of non-missing subjects. For subjects missing “post”, impute using MAX(post) from non-missing subjects.

---

3. Median Imputation: For subjects missing “pre”, impute using the MEDIAN(pre) of non-missing subjects. For subjects missing “post”, impute using MEDIAN(post) from non-missing subjects.

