## **3.6 SENSITIVITY ANALYSIS**

Sensitivity analyses will be conducted using an alternative baseline defined as the mean of all available pre-treatment measures. Selected exploratory endpoints will be repeated using the alternative baseline definition.

The sensitivity endpoints are as follows:

- Reachable Work Space (RWS) with and without weights
- Disease impact by subject report using FSHD-Rasch-built Overall Disability Scale (FSHD-RODS)
- Disease impact by subject report using FSHD-HI
- Physical function by Motor Function Measure (MFM) domain 1
- Manual Dynamometry
- Classic TUG and FSHD TUG
- Change in ambulation as measured by the 6-minute walking test (6-MWT)

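### The SAP fills missing main DUX4 composite scores with one group value, departs from the observed-pairs rule in Protocol 10.1.1, and attaches an SE that does not measure the precision of the filled estimate

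*SAP*

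**What the plan says.** Protocol 10.1.1 sets the rule for change summaries: "Summaries of change from baseline variables will include only subjects who have both a baseline value and corresponding value at the timepoint of interest".

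For the main DUX4 composite (the median of six standardised gene scores), the SAP does something else. Section 3.4.1 treats the assessment as missing if either biopsy result is unavailable, and then says: "Missing results will be imputed by mean, worst case, and median methods". Section 2.3.6 repeats this ("Missing composite score will be imputed by three methods as follows") and defines each method as one value taken from the group. For a missing on-treatment score under the mean method, for example, the instruction is "impute using MEAN(post) from non-missing subjects". The median method works the same way. The worst-case method uses the minimum pre-treatment score or the maximum on-treatment score.

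Neither section names a table of the main composite limited to subjects with both results, and neither says which of the three filled versions leads. SAP section 5, which lists major changes in the planned analyses, mentions only COVID-19 visit handling.

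Two other statements matter. SAP 2.1: "Standard error (SE) will be reported for all change from baseline tables", with no adjustment for filled values. SAP 3.4.1, on the alternative composites: "Composite scores based on simple averages will not be imputed".

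**The concern.** A score filled with a group mean or median carries no information about the subject it is assigned to, yet the table counts it as an observation. The SE printed beside the mean change is then computed as if all subjects had been measured. It describes neither the sampling error of the filled estimate nor that of the observed pairs.

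The main score is also checked against a 6-gene simple average, to see whether a simpler score leads to the same reading. That average is not imputed. With any missing result the two scores rest on different subjects, so a difference in scoring cannot be separated from a difference in who is included.

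The stakes are limited to how precise the DUX4 change looks. That still has some weight. DUX4 in muscle biopsies is the focus of the first interim analysis, and Protocol 1.3.4 says the results will guide further development. Missing scores were foreseen: the revision history for V1.1 reads "Added missing data handling rule for missing DUX4 composite score in section 2.3.5" (the rule now stands in 2.3.6), and V1.2 added the median method.

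**Working it through.** The plan states no SE, SD, correlation or missing count for this score, so it has no figure to reproduce. The check compares the SE that a filled table would report with the true sampling SE of the same mean change.

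**Inputs from the documents:** n = 14 enrolled (Protocol 4.1 and 4.4); fills computed from the non-missing subjects (SAP 2.3.6); an uncorrected SE in each change table (SAP 2.1).

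**Assumptions:** values missing completely at random; pre-treatment SD 1; on-treatment SD k; pre/on-treatment correlation r between 0 and 0.9; one or two subjects with a missing result.

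**Case 1: on-treatment value missing, mean fill.** Let c subjects have an on-treatment value. A filled value adds nothing to the on-treatment sum of squares or to the cross-products, but the table still divides by n and n-1:

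- Expected reported SE² = [(n-1) + (c-1)(k² - 2rk)] / [n(n-1)]
- True SE² = k²/c + (1 - 2rk)/n

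With equal SDs (k = 1) and n(n-1) = 182:

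| Missing | r | Reported SE | True SE | Ratio |
|---|---|---|---|---|
| 1 (c = 13) | 0 | √(25/182) = 0.371 | √(1/13 + 1/14) = 0.385 | 0.962 |
| 1 (c = 13) | 0.9 | √(3.4/182) = 0.137 | √(1/13 - 0.8/14) = 0.141 | 0.972 |
| 2 (c = 12) | 0 | √(24/182) = 0.363 | √(1/12 + 1/14) = 0.393 | 0.923 |
| 2 (c = 12) | 0.5 | √(13/182) = 0.267 | √(1/12) = 0.289 | 0.926 |
| 2 (c = 12) | 0.9 | √(4.2/182) = 0.152 | √(1/12 - 0.8/14) = 0.162 | 0.939 |

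The reported SE is therefore 3-4% too low with one value missing and 6-8% too low with two.

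With unequal SDs, two on-treatment values missing and r = 0.9:

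- k = 0.8: reported SE² = 4.2/182 = 0.0231; true = 0.64/12 - 0.44/14 = 0.0219; ratio 1.03, about 3% too large.
- k = 0.5: 5.85/182 = 0.0321 against 0.25/12 + 0.1/14 = 0.0280; ratio 1.07.
- k = 1.5: 8.05/182 = 0.0442 against 2.25/12 - 1.7/14 = 0.0661; ratio 0.82.

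**Case 2: the incomplete subjects miss both biopsies, mean fill.** Each filled change equals the mean observed change. With σ the SD of the change:

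- Reported SE² = (c-1)σ² / [n(n-1)]
- True SE² = σ²/c
- Ratio = √[c(c-1) / (n(n-1))]

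One subject missing: √(156/182) = 0.926. Two missing: √(132/182) = 0.852. Here σ cancels, so neither the SD ratio nor the correlation matters.

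**Simulation at k = 1.** Median fill gives nearly the same ratios: about 0.92-0.94 with two on-treatment values missing, 0.925-0.928 with one subject missing both, and 0.847-0.851 with two. Observed pairs give 0.997-1.005. If a reader built a nominal 95% interval from the filled SE, coverage would be about 93-95% with two on-treatment values missing and 90-91% with two subjects missing both.

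**The case against.** **Protocol 10.1.1 may still apply.** Protocol 10.4 leaves the detail of exploratory endpoints to the SAP, and one could read the observed-pairs rule as continuing beside the fills. The SAP does not say so. Its instruction for this score is specific and points the other way.

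**The effect is small.** An SE estimated from 14 subjects has a relative sampling error of about 1/√(2 × 13) = 20%, so a shift of 3-8% would rarely change how anyone reads a descriptive table. This stands, and it limits the weight of the point. It does not make the printed SE a measure of precision.

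**Other outputs soften it.** The simple-average composites are unimputed, no fill rule is stated for the single genes, and listings allow the observed pairs to be recovered. Three fills including a worst case give some range. The first interim analysis is triggered by subjects who completed the Visit 5 biopsy, so a missed second biopsy is largely excluded there. All of this stands as mitigation, but none of it corrects the main composite tables.

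**Stronger readings that the documents do not support:**

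- A reader might infer that the SE is too small whenever a result is missing. The direction depends on the SD ratio, the correlation and which biopsy is missing. Scores are scaled by pre-treatment variability only (SAP Appendix 4), so nothing forces equal on-treatment variability.
- A reader might infer that the filled SE is always below the observed-pairs SE, which is √[2(1-r)/c] at k = 1. With c = 12 the observed-pairs SE is 0.289 at r = 0.5 (filled 0.267) but 0.129 at r = 0.9 (filled 0.152, about 18% larger).
- A reader might cite SAP 3.6 ("Sensitivity analyses will be conducted using an alternative baseline defined as the mean of all available pre-treatment measures") because its list omits DUX4. DUX4 has one pre-treatment biopsy, so that analysis would change nothing, and its absence is not a gap.
- A reader might assume that fills come from the subject's own biopsy cohort, which would enlarge the effect in cohort tables. SAP 2.3.6 reads as all non-missing subjects.

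**Conclusion.** The point holds as a departure of the SAP from Protocol 10.1.1 that section 5 does not record. If any main composite score is missing, the mean- and median-filled tables carry an SE that does not describe the estimate beside it, and the comparison with the 6-gene simple average mixes scoring with subject set.

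The sizes above rest on an assumed missing count, on values missing at random and, for a single missing biopsy, on similar pre- and on-treatment SDs. When subjects miss both biopsies under mean fill, the 7% and 15% shortfalls need no assumption about SD ratio or correlation. The documents supply none of these inputs, so the direction for a single missing biopsy cannot be settled from them.

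The endpoint is exploratory, the SAP plans no test or interval for it, and no error rate is affected. If every subject has both results, nothing changes. This is worth fixing because it is cheap, not because it threatens the study's conclusions.

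**What to change.** In SAP 3.4.1, make the observed-pairs change (n, mean, SE) the main summary of the DUX4 composite, overall and by biopsy cohort, as Protocol 10.1.1 requires. This also puts the main score on the same subjects as the simple-average composites.

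Keep the mean, median and worst-case fills as labelled sensitivity tables that show the number imputed. Either omit the SE from them or mark it as not a valid measure of precision.

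The cost is SAP wording and one table. The downside is that n in the main summary falls if results are missing.
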